10.15.2 AEs of Special Interest

AEs of special interest (AESIs) will be identified from AE CRF page.

The following AEs are defined for this protocol as AESIs:

1. An overdose of pembrolizumab, as defined in section 6.7 of the protocol.
2. An elevated AST or ALT laboratory value that is greater than or equal to $3 \times \text{ULN}$ and an elevated total bilirubin laboratory value that is greater than or equal to $2 \times \text{ULN}$ and, at the same time, an alkaline phosphatase laboratory value that is less than $2 \times \text{ULN}$, as determined by way of protocol-specified laboratory testing or unscheduled laboratory testing.*

*Note: These criteria are based upon available regulatory guidance documents. The purpose of the criteria is to specify a threshold of abnormal hepatic tests that may require an additional evaluation for an underlying etiology. The trial site guidance for assessment and follow-up of these criteria can be made available. It may also be appropriate to conduct additional evaluation for an underlying etiology in the setting of abnormalities of liver blood tests including AST, ALT, bilirubin, and alkaline phosphatase that do not meet the criteria noted above. In these cases, the decision to proceed with additional evaluation will be made through consultation between the study investigators and the sponsor's medical monitor for the trial. However, abnormalities of liver blood tests that do not meet the criteria noted above are not AESIs for this trial.

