### **8.3.1.3 Adverse events of special interest**

The following AEs are defined for this Protocol as AESIs and must be reported to the sponsor or designee within 24 hours of awareness:

1. For patients without liver metastases or liver cancer or patients who do not receive hepatotoxic concomitant medications, the following AESIs must be reported:
  - a. On-treatment (i.e., from the first dose of study treatment to 90 days after the last dose of study treatment) ALT or AST increase that is greater than  $3\times$ ULN in combination with clinical jaundice
  - b. On-treatment ALT increase that is greater than or equal to  $3\times$ ULN and international normalized ratio increase that is greater than 1.5
  - c. Recurrence of CTCAE grade 3 ALT and/or AST increase in combination with total bilirubin increase greater than  $2\times$ ULN or greater than  $2\times$ baseline level
2. For patients with liver metastases or liver cancer or patients who receive hepatotoxic concomitant medications, the following AESIs must be reported:
  - a. On-treatment ALT or AST increase that is greater than  $5\times$ ULN in combination with total bilirubin increase greater than  $2\times$ ULN (of which more than or equal to 35% is direct bilirubin)

---

- b. On-treatment ALT or AST increase that is greater than  $5\times\text{ULN}$  in combination with clinical jaundice
- 3. An overdose of pembrolizumab, as defined in section [6.7](#)
- 4. An elevated AST or ALT laboratory value that is greater than or equal to  $3\times\text{ULN}$  and an elevated total bilirubin laboratory value that is greater than or equal to  $2\times\text{ULN}$  and, at the same time, an alkaline phosphatase laboratory value that is less than  $2\times\text{ULN}$ , as determined by way of Protocol-specified laboratory testing or unscheduled laboratory testing\*

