\*Note: These criteria are based upon available regulatory guidance documents. The purpose of the criteria is to specify a threshold of abnormal hepatic tests that may require an additional evaluation for an underlying etiology. The trial site guidance for assessment and follow-up of these criteria can be made available. It may also be appropriate to conduct additional evaluation for an underlying etiology in the setting of abnormalities of liver blood tests including AST, ALT, bilirubin, and alkaline phosphatase that do not meet the criteria noted above. In these cases, the decision to proceed with additional evaluation will be made through consultation between the study investigators and the sponsor's medical monitor for the trial.

However, abnormalities of liver blood tests that do not meet the criteria noted above are not AESIs for this trial.

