6.1 Changes from Protocol

The following changes to the protocol have been applied:

Endpoint of “Circulating tumor cell (CTC) count conversion from >5 to <5 cells per 7.5 mL of blood” for metastatic castration-resistant prostate cancer (mCRPC) only will be analyzed as a conversion from ≥ 5 to <5 cells per 7.5 mL of blood.

Endpoint of “Confirmed PSA decline of $\geq 50\%$ ” will not only evaluate the response at 6 months post-trial entry: all timepoints will be considered as per the schedule of assessments (Section 1.3.3 of Study Protocol).

Additional sensitivity analyses and exploratory endpoints:

As a sensitivity analysis for Best Overall Response (BOR) as per RECIST 1.1: BOR will also be performed as per Prostate Cancer Clinical Trials Working Group 3 (PCWG3)-modified RECIST 1.1 to study the effect of progressive disease in bone on the BOR, for patients with mCRPC.

As a sensitivity analysis to Clinical Benefit Rate (CBR) as per RECIST 1.1: CBR will also be performed for all patients in mCRPC – with both measurable and non-measurable disease – as per PCWG3-modified RECIST 1.1, to study the effect of progressive disease in bone on the CBR.

Other sensitivity analyses using All Subjects as Treated (ASaT) population on selected efficacy endpoints.

As per the EMA guideline on the evaluation of anticancer medicinal products in man, the endpoint PFS2 has been added as an exploratory endpoint.

Following Futility Analysis in August 2023, recruitment to the study was stopped. Exploratory Endpoints will no longer be analyzed.

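### SAP 10.15.2 lists two of the protocol's seven AESI criteria, omits five liver criteria, and does not declare the difference

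*SAP*

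**What the plan says.** Protocol section 8.3.1.3 sets out four numbered AESI items that hold seven separate criteria.

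- Item 1 opens "For patients without liver metastases or liver cancer or patients who do not receive hepatotoxic concomitant medications, the following AESIs must be reported" and has three parts: (a) raised ALT or AST with clinical jaundice; (b) raised ALT with an INR above 1.5; (c) "Recurrence of CTCAE grade 3 ALT and/or AST increase in combination with total bilirubin increase greater than" twice the ULN or twice the baseline level.
- Item 2 opens "For patients with liver metastases or liver cancer or patients who receive hepatotoxic concomitant medications, the following AESIs must be reported" and has two parts, both with a higher transaminase threshold: (a) with raised, partly direct bilirubin; (b) with clinical jaundice.
- Item 3 is pembrolizumab overdose.
- Item 4 is ALT or AST at least 3 × ULN with total bilirubin at least 2 × ULN and ALP below 2 × ULN.

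A note after item 4 ends by saying that "abnormalities of liver blood tests that do not meet the criteria noted above are not AESIs for this trial".

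SAP section 10.15.2 first says "AEs of special interest (AESIs) will be identified from AE CRF page". It then states "The following AEs are defined for this protocol as AESIs" and lists two items, which are protocol items 3 and 4. The protocol's note follows, with the same closing sentence.

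SAP sections 4.0 and 6.0 name Protocol Amendment 1 of 20 April 2023 as the governing version. SAP section 6.1, under "The following changes to the protocol have been applied", covers circulating tumor cells, PSA, added sensitivity analyses, PFS2 and the dropped exploratory endpoints. It does not mention AESIs.

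**The concern.** The SAP claims to state the protocol's AESI definition but gives only part of it, without saying so. The closing sentence makes this more than an omission. Placed after two criteria, it says that a liver abnormality outside those two is not an AESI, including abnormalities that the protocol requires sites to report as AESIs.

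AESIs belong to the secondary safety endpoint in protocol section 3 and SAP section 7.4, and SAP section 12.8.1.1 gives them a dedicated table and listing. A programmer or medical reviewer working from the SAP has no rule for an event that a site flags under the protocol and that the SAP text calls a non-AESI. Criteria 2a and 2b apply to patients with liver cancer, and hepatocellular carcinoma is one of the six planned cohorts.

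**Working it through.** The plan gives no figure to reproduce. The check has three parts: a count, a test of whether SAP item 2 already covers the omitted criteria, and a look at which other outputs would show the events.

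**Count.** Protocol: 3 (1a–1c) + 2 (2a–2b) + 1 (item 3) + 1 (item 4) = 7 criteria. SAP: 2. Missing: 7 − 2 = 5, all hepatic. By numbered item, the SAP has 2 of 4.

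**Coverage by SAP item 2.** SAP item 2 requires all three of: ALT or AST ≥ 3 × ULN, total bilirubin ≥ 2 × ULN, and ALP < 2 × ULN. For each omitted criterion I looked for a case that meets the protocol and fails SAP item 2. Values are illustrative multiples of ULN, except INR. Cases for item 1 have no liver metastases or liver cancer and no hepatotoxic drug; cases for item 2 have liver metastases and a hepatotoxic drug, so group membership is not in doubt.

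| Protocol criterion | What it requires | Case | Why SAP item 2 fails |
|---|---|---|---|
| 1a | ALT or AST > 3, jaundice | ALT 4, jaundice, bilirubin 3, ALP 2.5 | ALP 2.5 is not < 2 |
| 1b | ALT ≥ 3, INR > 1.5 | ALT 4, INR 1.8, bilirubin 1, ALP 1 | bilirubin 1 is not ≥ 2 |
| 1c | recurrent grade 3 ALT/AST, bilirubin > 2 × ULN or > 2 × baseline | recurrent ALT 6, bilirubin 1.2 from baseline 0.5 (1.2 / 0.5 = 2.4 × baseline), ALP 1 | bilirubin 1.2 is not ≥ 2 |
| 2a | ALT or AST > 5, bilirubin > 2 with ≥ 35% direct | ALT 6, bilirubin 2.5 with 50% direct, ALP 2.5 | ALP 2.5 is not < 2 |
| 2b | ALT or AST > 5, jaundice | ALT 6, jaundice, bilirubin 3, ALP 2.5 | ALP 2.5 is not < 2 |

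None of the cases is an overdose, so SAP item 1 does not apply either. Result: 5 of 5 omitted criteria admit a case that the SAP list does not capture.

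The converse also holds. Set bilirubin to 2.5 and ALP to 1 in the same five cases, and 5 of 5 meet SAP item 2. The overlap is therefore partial for every omitted criterion: never absent and never complete.

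**Other outputs.** SAP section 12.8.2.2 has a Hy's law summary with the same three conditions as item 2, so it adds nothing for these cases. Its eDISH figure needs ALT or AST at 3 × ULN and bilirubin at 2 × ULN, with no stated ALP limit. It would show the example cases for 1a, 2a and 2b, but not 1b (bilirubin 1) or 1c (bilirubin 1.2). INR is collected (protocol section 8.2.5.1), but D-dimer is the only coagulation test selected for summary in SAP section 12.8.2.1, so INR would appear only in listings. Unflagged events would also remain in the general AE outputs if recorded as AEs, and in the abnormal-laboratory and all-data listings. None of these outputs labels them as AESIs.

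**The case against.** The strongest objection is that the list is not the operative rule. The SAP takes AESIs from the AE CRF page. Sites identify them under protocol section 8.3.1.3 and report them through the eCRF (protocol section 8.3.8.4), the SAP is to be read with the protocol, and no SAP text filters flagged events through the two items. A correctly flagged event may therefore reach the table and listing whatever the list says. This stands as a limit: no loss of events is shown. It does not remove the contradiction within section 10.15.2. It also depends on a CRF that is not among the documents. The CRF version cited in SAP section 6.0 is dated 28 February 2022, before Amendment 1 and before the regulator's requirement of 16 May 2022 that the amendment log gives as the origin of the liver reporting instructions (change 38). Whether its AESI field covers all seven criteria is unknown.

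A second objection concerns the closing sentence. In the protocol the note hangs by an asterisk on item 4 alone, so the sentence can be read as a footnote to that item and is already awkward beside items 1 and 2. That is fair, and the SAP copied the wording rather than inventing it. But in the protocol the other five criteria are still on the page as AESIs. In the SAP they are not, so under either reading its text excludes those of their events that fall outside item 2.

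Third, the eDISH figure gives some hepatic coverage, the analyses are descriptive, the primary ORR analysis is untouched, and recruitment has stopped. All true, and they bound the consequence. They do not make the stated definition of a named secondary safety endpoint correct.

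Finally, the mismatch looks like carried-over text rather than a decision: SAP section 8.0 also keeps eligibility wording that differs from the current protocol section 5.1. That is plausible, and it supports correcting the list.

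**Conclusion.** The concern holds. In a SAP written to Amendment 1, section 10.15.2 states 2 of the protocol's 7 AESI criteria (2 of 4 numbered items), omits five liver criteria that its own item 2 covers only in part, and declares no AESI change in section 6.1. It should be fixed.

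The size is that of a definition, not of a result: 5 of 7 criteria are missing, and the number of affected events cannot be estimated from the documents. Effect on the AESI outputs depends on whether the CRF field covers all seven criteria, whether sites flag accordingly, and whether the outputs use that flag without applying the SAP list. If all three hold, the outputs may be complete and only the text is wrong. If not, protocol-defined AESIs would go unlabelled.

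**What to change.** Before database lock:

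1. Replace the list in SAP section 10.15.2 with all seven criteria of protocol section 8.3.1.3, so that the closing sentence refers to the full set. If the narrower list is intended, declare and justify it in SAP section 6.1.
2. Confirm that the AESI field on the AE CRF page covers all seven criteria, and state that the AESI table and listing use that flag.

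Optionally, run a laboratory check that queries unflagged candidates for criteria 1b, 1c, 2a and 4, taking liver-disease and hepatotoxic-drug status from site data. The wording of protocol items 1 and 2 lets a patient fall in both groups (for example, liver metastases but no hepatotoxic drug); such patients should be assessed against both sets.

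The cost is low: the text of one SAP section and one check of the AE CRF page. The laboratory check is extra work and is not needed to resolve the contradiction.

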10.15.3 Physical Examinations, ECGs, and Other Observations Related to Safety

Additional safety assessments include physical examinations, ECOG, ECG measurements including left ventricular ejection fraction (LVEF), and pregnancy test.

10.16 Handling of Missing Data

No imputation of missing data will be performed other than specified in this section.

10.16.1 Imputation of Missing Dates for AEs and Concomitant Medication and Procedures

For the purposes of assigning AEs and concomitant medications to study periods the following algorithm will be used for missing or partial dates (AE start/stop dates and concomitant medication start/stop dates):

The actual (non-imputed) value for date will be presented in all data listings and imputed dates will only be used for programming purposes, such as TEAE derivation.

Start date

If the start date is completely missing (i.e., the day, month, and year are all unknown), the start date will be set to the date of the first dose of study medication

Missing day only

- If the month and year of the incomplete date are the same as the month and year of the **first dose date**, then the day of the **first dose date** will be assigned to the missing day.
- If either the year is before the year of the **first dose date** or if years are the same but the month is before the month of the **first dose date**, then the last day of the month will be assigned to the missing day.
- If either the year is after the year of the **first dose date** or if both years are the same but the month is after the month of the **first dose date**, then the first day of the month will be assigned to the missing day.

Missing month only

- The day will be treated as also missing and both month and day will be replaced according to the below procedure.

Missing day and month

- If the year of the incomplete date is the same as the year of the **first dose date**, then the day and month of the **first dose date** will be assigned to the missing fields.
- If the year of the incomplete date is not the same as the year of the **first dose date**, then January 1 will be assigned to the missing fields.

If the stop date is complete and the imputed start date is after the stop date, then the start date will be imputed using the stop date

Stop date

Missing day only

- If the month and year of the incomplete date are the same as the month and year of the **last visit date**, then the day of the **last visit date** will be assigned to the missing day.
- If either the year is before the year of the **last visit date** or if both years are the same but the month is before the month of the **last visit date**, then the last day of the month will be assigned to the missing day.
- If either the year is after the year of the **last visit date** or if both years are the same but the month is after the month of the **last visit date**, then the first day of the month will be assigned to the missing day.

Missing month only

- The day will be treated as missing and both month and day will be replaced according to the below procedure.

Missing day and month

- If the year of the incomplete date is the same as the year of the **last visit date**, then the day and month of the **last visit date** will be assigned to the missing fields.
- If the year of the incomplete date is before the year of the **last visit date**, then 31st December will be assigned to the missing fields.
- If the year of the incomplete date is after the year of the **last visit date**, then 1st January will be assigned to the missing fields.

Completely missing stop dates where a record is not ongoing, will not be imputed.

Incomplete start dates of follow-up anti-cancer therapy will be imputed as follows:

- If only 'day' is missing, then impute with the first day of the month.
- If 'day' and 'month' are missing and 'year' is not missing and is the same as the year of the last dose, then impute as date of last dose.
- If the imputed start date is greater than the last contact date, then set to the last contact date.

Incomplete dates of death will be imputed as follows:

- If only 'day' is missing, then impute with the first day of the month.
- If 'day' and 'month' are missing and 'year' is not missing and is the same as the year of the last contact date, then impute as the date of the last contact +1 day.
- If 'day' and 'month' are missing and 'year' is not missing and is greater than the year of the last contact date, then impute as 1st January of that year.
- If the imputed death date is less than the last contact date, then set to the last contact date + 1 day.

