## 7 DISCONTINUATION OF STUDY INTERVENTION AND PATIENT DISCONTINUATION/WITHDRAWAL

### 7.1 Discontinuation of study intervention

Discontinuation of study interventions does not represent withdrawal from the study.

A patient must be discontinued from study interventions but continue to be monitored in the study (if possible) for any of the following reasons:

- Confirmed radiographic disease progression (please refer to section 10.2)
- Clinical disease progression (investigator's assessment)
- AE (intercurrent illness or study intervention-related toxicity that would, in the judgment of the investigator, affect assessments of the patient's clinical status to a significant degree or require discontinuation of study interventions)
- Patient may withdraw from the study at any time for any reason; the investigator must make every effort to determine the reason for this decision and record it in source documentation of the patient
- Discontinuation of treatment may be considered for patients who have attained a confirmed complete response (CR) and have been treated for at least 8 cycles (at least 24 weeks), receiving 2 cycles of the combination including 2 doses of pembrolizumab and at least 80% of the planned doses of nanrilkefusp alfa beyond the date when the initial CR was declared
- Any study intervention-related toxicity specified as a reason for permanent discontinuation as defined in the guidelines for dose modification due to AEs in section 6.5
- Death of the patient
- Pregnancy of the patient
- Concomitant treatment with a prohibited medication, including further lines of systemic anti-cancer therapy (also see section 6.8.2)
- Patient's non-compliance
- Lost to follow-up
- Study terminated by the sponsor

Pembrolizumab will be discontinued after the completion of 35 administrations (approximately 2 years; also see section 6.6).

In case nanrilkefusp alfa needs to be discontinued for reasons other than disease progression, pembrolizumab treatment can continue for up to a total of 35 administrations (approximately 2 years) in patients without disease progression or unacceptable toxicity. In case pembrolizumab needs to be discontinued, nanrilkefusp alfa treatment can continue until disease progression or unacceptable toxicity (not applicable in the Czech Republic). In the Czech Republic: In case pembrolizumab needs to be discontinued, nanrilkefusp alfa treatment will be discontinued as well.

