10.13.8 Progression-Free Survival (PFS and iPFS)

- Per RECIST (v1.1): A PFS time is defined as the time from the first day of study treatment until the first date of radiological disease progression (PD) or death.

- Per iRECIST: An iPFS time is defined as the time from the first day of study treatment until the first date of confirmed disease progression or death. The date of disease progression would be the date of the first iUPD that is confirmed by a later iCPD. This can occur on the subsequent assessment or after a series of persistent iUPD assessments. The date of iUPD will also be used as disease progression if the iUPD assessment is followed by:
 - if the patient stops protocol treatment because they were judged to be clinically unstable, or
 - no further tumor assessments are done, or
 - if the next timepoint responses are all iUPD, and iCPD never occurs, or
 - if the patient dies from their cancer.

An iUPD assessment followed by subsequent non-PD assessments will not be considered as the start of progression. Stopping protocol treatment due to clinical instability is identified as subjects discontinuing from SOT101 with reason 'clinical progression'.

- Per PCWG3-modified RECIST 1.1: PFS time is defined as the time from the first day of study treatment until the date of PCWG3-modified RECIST 1.1 defined confirmed disease progression or death.

Clinical deterioration alone will not be considered as documented disease progression. Only tumor assessments performed before the start of any new anti-cancer treatment (including radiation therapy to the tumor lesion (s)) will be considered in the assessment of PFS/iPFS.

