12.7.6 PFS and iPFS

PFS/iPFS will be summarized using Kaplan-Meier estimates for each indication separately. A sensitivity analysis will be performed using the ASaT population.

PFS will be calculated based on PCWG3-modified RECIST for the mCRPC cohort for those patients with both measurable and non-measurable disease.

Patients with missing data will be censored/considered as having an event as specified below:

Situation	Date of progression or censoring	Outcome
Incomplete or no baseline tumor assessments.	Date of the first day of study treatment	Censored
Start of new anti-cancer therapy.	Date of the last tumor assessment with non-progression before the start of new anti-cancer therapy.	Censored
Death before the first disease progression assessment.	Date of death.	Progressed

Situation	Date of progression or censoring	Outcome
Death between adequate tumor assessment visits.	Date of death.	Progressed
Progression or death after one (consecutively) missed adequate tumor assessment ^a .	Date of progression or death, whichever is earliest (if both occur).	Progressed
Progression or death after more than one (consecutively) missed adequate tumor assessments.	Date of the last evaluable tumor assessment.	Censored
No progression, no death.	Date of the last evaluable tumor assessment, or first date of study treatment if no post-baseline tumor assessments.	Censored

^aIdentified as 12 weeks between the date of last evaluable tumor assessment and the date of the event.

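### Imputed start dates of new anti-cancer therapy have no floor, so a documented progression scan can be dropped and PFS or DoR censored where an event occurred

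*SAP*

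**What the plan says.** SAP 10.16.1 has a separate block for the start of follow-up therapy: "Incomplete start dates of follow-up anti-cancer therapy will be imputed as follows". It contains three rules.

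- Day missing: "If only 'day' is missing, then impute with the first day of the month".
- Day and month missing, where the recorded year "is the same as the year of the last dose, then impute as date of last dose".
- A cap: "If the imputed start date is greater than the last contact date, then set to the last contact date".

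Nothing ties the imputed start to the last study dose, the last tumor assessment or the date of progression. The block for death dates that follows does have a lower limit: "If the imputed death date is less than the last contact date, then set to the last contact date + 1 day".

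The therapy start date decides which scans count. For PFS and iPFS, SAP 10.13.8 admits "Only tumor assessments performed before the start of any new anti-cancer treatment". For DoR and iDoR, SAP 10.13.6 is slightly wider and also admits a scan on the start date itself. The PFS table in SAP 12.7.6 censors a patient who starts new therapy at the "Date of the last tumor assessment with non-progression before the start of new anti-cancer therapy". The BOR window in SAP 10.13.3 also closes at the start of new therapy.

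Protocol 7.1 lists among the reasons for stopping study treatment: "Concomitant treatment with a prohibited medication, including further lines of systemic anti-cancer therapy".

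**The concern.** New therapy often follows progression, so the PD scan and the therapy start can lie close together. If the start date is partial, the day-missing rule moves it to the earliest day the record allows. That day can fall before the PD scan that led to the change of therapy. The scan then counts as taken after new therapy and is disregarded.

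The imputed day can also fall before the last study dose, which sits badly with Protocol 7.1. The year-only rule cannot do that, because it uses the last dose date itself. It can still precede a PD scan taken after the last dose, and Protocol 8.1.1.3 allows the discontinuation scan up to 4 weeks after stopping.

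The patients affected are those who progressed. Replacing their event by censoring at an earlier scan is informative, and it acts in one direction: towards longer PFS and DoR.

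**Working it through.** The plan states no figure on this point, so there is none to reproduce. The check has four steps.

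**1. Trace the rules through an example.** All dates are in one non-leap year. Last non-PD scan 27 January; last study dose 9 March; PD scan 10 March (42 days after 27 January); new therapy 20 March, recorded only as March.

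- Imputed start: 1 March. This precedes the last study dose and the PD scan.
- SAP 10.13.8 keeps scans before 1 March, so the PD scan is dropped.
- SAP 12.7.6 censors PFS at 27 January. The true result is an event on 10 March.

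Now suppose only the year is recorded and the PD scan is on 20 March. The imputed start is 9 March and the scan is again dropped. Under the year-only rule a PD scan is lost if it falls on or after the last dose (PFS), or after it (DoR).

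For DoR, the new-therapy row in SAP 12.7.4 applies only to patients without progression or death. The loss therefore comes from the scan filter in 10.13.6: once the PD scan is excluded, a living patient falls into that row.

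**2. Share of day-missing records in which the PD event is lost.** Let *g* be the number of days from PD scan to true therapy start. Assume the true start is equally likely on each day of 2023. The PFS event is lost when the PD scan falls on or after the 1st of the month of therapy start. The DoR event is lost when it falls after the 1st.

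- PFS, for *g* up to 28: (365 − 12*g*)/365. At *g* = 14 this is (365 − 168)/365 = 197/365 = 54%.
- DoR, for *g* up to 27: (365 − 12(*g* + 1))/365. At *g* = 14 this is 185/365 = 51%.
- At *g* = 28, DoR is counted directly: 7 months of 31 days give 2 days each and 4 months of 30 days give 1 each, so 18/365 = 5%.

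| Gap *g* (days) | PFS event lost | DoR event lost |
|---|---|---|
| 7 | 77% | 74% |
| 14 | 54% | 51% |
| 21 | 31% | 28% |
| 28 | 8% | 5% |
| 31 or more | 0% | 0% |

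At 31 days or more, the scan and the therapy start cannot share a calendar month.

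**3. Share of all PD events followed by new therapy.** The frequency of partial dates is not in the documents. Assume 5-10%, all of them day-missing.

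- Low end: 5% × 8% = 0.4%.
- High end: 10% × 77% = 7.7%.

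This covers gaps of 7 to 28 days. For gaps of 31 days or more the loss is nil.

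**4. Illustrative effect on PFS.** Assumptions: exponential progression with median 91 days, scans every 42 ± 14 days, *g* = 14, every progressor starts new therapy, 20,000 simulated patients.

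| Day-missing share | Events lost per 50 patients | 6-month PFS | Median PFS (days) |
|---|---|---|---|
| 0% | 0 | 27.9% | 117 |
| 5% | 1.2 | 28.5% | 119 |
| 10% | 2.6 | 29.3% | 120 |
| 20% | 5.2 | 30.8% | 123 |
| 30% | 7.7 | 32.4% | 126 |

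When step 2 is rerun with the imputed start set to the later of the 1st of the month and PD + 1 day, no PFS events are lost at *g* = 7, 14 or 21.

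**The case against.** **The rule may not be meant for efficacy.** SAP 10.16.1 is titled for adverse events, concomitant medication and procedures, and its stated purpose is to assign records to study periods. New-therapy start does delimit those periods (SAP 10.6). The SAP nowhere says that the imputed date feeds PFS or DoR. That stands as a gap in wording. But SAP 10.16 excludes any imputation outside that section, and PFS, DoR and BOR all need this date, so use there is the natural reading. If it is not intended, the SAP has no rule for partial dates in those endpoints.

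**The gap is often long.** Clinically stable patients continue treatment and are rescanned 4 to 8 weeks after first progression (Protocol 8.1.1.2 and 10.2.2). RECIST 1.1 PD is dated to the first iUPD (SAP 10.13.1). For these patients new therapy often follows by 28 days or more, where the day-missing loss is 8% or less. If they are dosed after the first iUPD, the year-only rule leaves that scan in place too. This stands. The 7- to 21-day figures apply mainly to clinically unstable patients and early discontinuations.

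**The effect is small and the endpoints are secondary.** With 5-10% day-missing, the simulated median moves by 2 to 3 days against a scan window of ± 14 days. The analysis is descriptive (SAP 12.0) and recruitment has stopped (SAP 6.1). This limits the importance. It does not make the rule right: only exploratory endpoints were dropped, and PFS and DoR are still to be reported in small cohorts.

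**A floor at PD imputes from the outcome.** A PD that truly followed an early switch of therapy would be counted as an event. This is fair, and is the reason for the sensitivity analysis below.

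**Conclusion.** The point holds. The therapy-start rules can convert a documented progression into a censored observation, and the day-missing rule can place new therapy before the last study dose. The bias is towards longer PFS and DoR. Its size depends on two quantities that the documents do not give: the share of partial dates and the gap from PD to new therapy. Under the assumptions above it is about 0.4-8% of PD events followed by new therapy, and nil for day-missing dates at gaps of 31 days or more. It is worth correcting, but is not a threat to the primary endpoint.

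Three stronger readings are tempting and are not supported.

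- *Both rules impute as early as possible.* Only the day-missing rule does. The year-only rule uses the last dose date, not 1 January.
- *iPFS and iDoR are affected to the same degree.* SAP 10.13.6 and 10.13.8 date the event to the first iUPD, and count it even without confirmation if no further scans are done or treatment stops for clinical progression. Dropping a later iCPD scan generally leaves the event in place. It is lost only when the iUPD scan itself is dropped.
- *ORR is distorted.* In a patient who responded and then progressed, the confirmatory scan precedes the PD scan and would rarely fall in the month of new therapy. The main change is a BOR of PD becoming NE, and neither is a response.

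**What to change.** Keep the present rules in SAP 10.16.1 and add a floor:

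- The imputed start is not earlier than last study dose + 1 day.
- Where PD is documented within the month or year of the partial date, it is not earlier than PD date + 1 day.
- The date stays within the recorded month or year and remains capped at last contact, but the cap may not move it back to or before a documented PD. If the PD scan is on the last day of the recorded period, no later date is left inside it, so the text should say directly that the scan is kept.

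State that this date is used for PFS, DoR and BOR. Add a sensitivity analysis with the floor at last dose only. It would show how far the results depend on the PD floor, whose known downside is counting a PD that truly followed an early switch.

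There is no need to move to end-of-month or 31 December imputation. That is a more debatable change, and the floor already removes the fault.

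A related gap can be closed in the same edit: no rule covers a year-only start in a year later than that of the last dose.

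The cost is a few lines of SAP text and minor programming. No new data are needed.
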